## 6.2 Evaluation of Adverse Events

Patients will be assessed for treatment related adverse events weekly during on treatment visit during radiation therapy, at the pre-operative evaluation visit and at follow up visits for at least 5 years. Additional patient visits may be needed as clinically indicated. At these visits, study staff will assess adverse events by recording all voluntary complaints of the subject and by assessment of clinical, radiologic and laboratory features as indicated by the schedule in Appendix B and as clinically warranted. At each study visit, the subject should be questioned directly regarding the occurrence of any adverse experience since his/her last visit.

## 6.3 Documentation of Adverse Events

All adverse events, whether observed by the Investigator, elicited from or volunteered by the subject, will be documented. Each adverse event will include a brief description of the experience, the date of onset, the date of resolution, the duration and type of experience, the severity, and the relationship to SBRT, contributing factors, and any action taken with respect to the planned radiation therapy. In addition, any toxicity leading to radiation treatment break and delay in surgical resection beyond 3 weeks post SBRT will be noted.

All patients are expected to undergo surgical resection within 3 weeks after radiation therapy. Any Intraoperative complications including blood loss, total operative time and amount of fibrosis noted by the surgeon will be recorded in the operative report. Post-operative complications including delayed wound healing, blood loss, infection, length of hospital stay, incidence of pancreatic leak, hospital readmissions for complications will also be recorded. Appendix A lists the data the surgical oncology team is responsible for recording.

Treatment related late complications including but not limited to duodenal and intestinal ulceration, perforation, gastritis, bowel adhesions and obstruction, will be recorded at follow ups up to 5 years after treatment.

## 6.4 Serious Adverse Events (SAEs)

A serious adverse event is any adverse event that results in any of the following outcomes:

- death;
- is life-threatening;
- requires inpatient hospitalization or prolongation of existing hospitalization;
- results in persistent or significant disability/incapacity;
- is a congenital anomaly/birth defect; or
- requires medical or surgical intervention to prevent permanent impairment or damage.

Any serious adverse events will be communicated directly to the primary investigator ([name]) within 24 hours and documented in the patient's medical chart. [name] will determine how to respond to the event and whether the patient will continue on the study.

All SAEs will be reported to the IRB per local institutional policy.

## 6.5 Treatment Modification due to adverse events

We do not anticipate any serious treatment related adverse events will take place during or immediately following SBRT treatment. We expect that the most common acute toxicities of radiation therapy will be mild nausea, fatigue and loose bowel movements.

Patients will finish planned radiation if they experience up to grade 2 treatment related toxicity. If patients develop any serious adverse event or any grade 3 or higher treatment related toxicity, SBRT radiation will be stopped and the patients will proceed directly to surgical resection if deemed appropriate by surgical oncology.

## 7. RISK/BENEFIT ASSESSMENT

This study is being conducted because the investigators believe that treating pancreatic adenocarcinoma with preoperative SBRT may improve outcome compared with more conventional treatment. There have been several small-scale studies at other institutions (as documented in the introduction) which have shown delivering SBRT to the pancreas can be safe and effective. However, this technique has not been attempted at URMC. We aim to study whether neoadjuvant SBRT is feasible at URMC. There are benefits and risks associated with this study as documented below. The investigators believe that the benefits outweigh the potential risks for patients enrolled on this study.

### 7.1 Benefits of Participation

- a) In conventional treatment, radiation is delivered to the surgical bed which contains a large of bowel that has been surgically manipulated. This study calls for radiation to be delivered prior to surgery. This allows the radiation to be targeted at the gross tumor directly which will decrease the amount of normal bowel that is treated. In addition, the tumor vascular supply preoperatively is generally more robust than postoperatively allowing better oxygenation to the tissue which is critical for the tumoricidal effect of radiation.
- b) In conventional treatment, radiation is delivered in conjunction with radio-sensitizing chemotherapy over a period of 5-6 weeks. This chemotherapy is generally not as effective at controlling micrometastatic disease compared to definitive chemotherapy which may increase the risk of metastatic progression. This study calls for a shorter

course of radiation treatment to be delivered over 1-2 weeks preoperatively. This will allow the patient to receive full dose chemotherapy without interruption after surgery. This could reduce the risk of metastatic disease which is a major problem in the treatment of pancreatic cancer.

- c) Conventional radiation treatment delivers a small dose of radiation spread over 5-6 weeks. It is known that pancreatic cancer is relatively resistant to radiation therapy. The radiation in this study is delivered in larger doses over a shorter period of time which may help to overcome some of the resistance of pancreatic cancer.

## 7.2 Risks of Participation

- a) Preoperative SBRT could cause toxicities that could delay or even prevent surgical resection which is the most important treatment for resectable pancreatic cancer. However, previous studies have demonstrated that the vast majority of patients who undergo preoperative radiation can safely undergo surgery in a timely fashion.
- b) Radiation therapy can cause both acute and delayed side effects. Acute side effects that take place during or immediately after treatment can include fatigue, nausea, vomiting, diarrhea, loss of appetite and weight loss. These effects are expected to be uncommon and can be managed with supportive care such as anti-nausea or anti-diarrheal medicines. Delayed side effects can take place months to years after radiation and can include delayed wound healing, scar tissue formation and bowel obstruction and structuring. These effects are expected to be very rare. These effects are expected to be similar or decreased compared with the toxicities associated with conventional radiation.
- c) There is a risk of invasion of patient privacy. All the information gathered from patient chart or records, including name and any other identifying information will be strictly confidential and will be kept under lock and key. The patients will not be identified nor will any information that would make it possible for anyone to identify the patient be used in any presentation or written reports about this study. Only summarized data will be presented at meetings or in any publications.

## 8. CONFIDENTIALITY OF DATA AND INFORMATION STORAGE

All protected health information will be de-identified prior to storage in the research database. Subjects in the research database will be only identified by an ID number based on their order of enrollment (i.e. Subject 1, Subject 2 etc.). The primary investigator, [name] will maintain a password-protected file that will link the subject ID code to the patient's medical record number in the electronic medical record system at URMC. All research data will be kept in

secure data servers in the department of radiation oncology. All research spreadsheets will have passwords protection that will only be known to the study investigators.

The patient's enrollment on the trial and any clinical data relevant to the patient's care will be documented in the patient's electronic medical record at URMC.

## **9. DATA ANALYSIS AND MONITORING**

The purpose of this pilot study is to determine feasibility of preoperative SBRT followed by surgical resection at URMC and to determine its safety and tolerability in a small population of patients. For this phase 1 trial, we plan to enroll 18 patients over 1-2 years with a goal of 12 evaluable cases. This is a generally accepted number of patients for phase 1 trials and will minimize the risks to patients in case the treatment is found to be unsafe. We will stop recruitment and analyze the safety data if there appears to be any grade 3 or greater toxicity on any subject that can be directly attributed to SBRT or if any patients are made ineligible for surgical resection solely due to toxicities from SBRT.

In the case where any patient becomes ineligible for resection due solely to toxicity from SBRT, the study will be immediately closed to accrual. We will stop recruitment and any patient who has not started radiation therapy will have their planned radiation treatment canceled. A patient who has started radiation therapy will undergo an individual discussion with [name] about the risks and benefits of continued treatment.

If a patient experiences grade 3 or greater toxicity directly attributable to SBRT that is reversible and ultimately able to undergo resection, we will analyze the event and attempt to prevent/reduce the adverse event from taking place again. We will discuss the risks and benefits of continued recruitment into the study with our co-investigators and determine whether or not to continue the study. If we believe that modifications can be made that will reasonably reduce the risk of a future event from occurring, we will continue recruitment to the study.

The investigators plan to evaluate the rates of acute toxicity after 12 patients have been enrolled and undergone SBRT and surgical resection. Long term safety and efficacy will be evaluated after all 12 patients have undergone surgical resection and have either been followed for at least 6 month or have died. The primary investigator, [name] will have access to all of the study data.

The Cancer Center Data & Safety Monitoring Committee will monitor the study for safety. Study

Investigators will conduct continuous review of data and patient safety. The Investigator will submit quarterly progress reports of these data to the Clinical Trials Monitoring Committee for review [Appendix C]. The review will include for each treatment arm/dose level: the number of patients enrolled, withdrawals, significant toxicities as described in the protocol, serious adverse events both expected and unexpected, dose adjustments, and responses observed. The PI maintains a database of all adverse events with toxicity grade and information regarding treatment required, complications, or sequelae. The Investigator will submit a copy of the AE spreadsheet along with the Progress Report to the Clinical Trials Monitoring Committee for review. Actual review dates will be assigned when the 1st patient is accrued.

- Any serious adverse event that is serious, related AND unexpected must be reported within 10 calendar days to both the Safety Coordinator and the RSRB (see RSRB guidelines). The DSMC Chair will determine whether further action is required, and when patient safety is of concern, an interim meeting may be called.
- Serious adverse events that are related AND expected or unrelated AND unexpected will be reported to the Committee for review at the quarterly meeting. SAE reports are expected to include sufficient detail so that the DSMC can determine the severity, toxicity grade, expectedness, treatment required, and a follow up report documenting resolution or if there are sequelae. Unless otherwise specified in the protocol, serious adverse events that require detailed reports (but not necessarily expedited) are expected, related, non-hematologic toxicities of grades 3, 4 or 5.

We plan to publish a descriptive analysis of the results including acute and late toxicity including surgical morbidity. We plan to report oncologic outcomes including median overall survival, progression free survival, local progression free survival and distant progression free survival. Analysis will be using Kaplan-Meier method. Survival time will be measured from the date of diagnosis. A local recurrence will be defined as any evidence of tumor recurrence within the PTV. Whether local recurrence occurred in conjunction with, before or after distant recurrence will be noted.

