## SCHEMA

Phase I: 12 patients who undergo SBRT and surgical resection

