##### **4.2 Evaluation during study Period**

- a) History, physical and vital signs during the weekly “on treatment visit” during radiation therapy
- b) History, physical and vital signs and laboratory evaluation obtained by surgery team prior to resection. Specific tests needed will be determined by surgical team.
- c) Following resection, patients will be assessed within 30 days after discharge for post-operative morbidity by the surgery team.
- d) Patients will be followed at least every 6 months for a minimum of 5 years by a physician from either radiation, surgical or medical oncology service. Closer follow up may be needed based on clinical situation.

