#### 4.3.3 Surgery

Surgery will be performed no more than 3 weeks after completion of radiation therapy. A pancreaticoduodenectomy (Whipple procedure) with standard lymphadenectomy will be done. Restaging is not required prior to surgery. However if re-staging scans are obtained and demonstrate metastatic disease, surgery will not be performed.

An attempted resection may also be aborted when more advanced or metastatic disease is found at the time of laparotomy. If surgical resection cannot be completed due to the presence of advanced disease, the patient will be withdrawn from the protocol at that time and will continue their care with standard treatment and follow up based on their clinical characteristic.

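### Patients withdrawn because resection could not be completed may leave study follow-up, and the plan commits to no resection rate although feasibility of SBRT followed by resection is its stated purpose

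*Combined protocol and SAP*

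**What the plan says.** The purpose is stated in Section 9: "The purpose of this pilot study is to determine feasibility of preoperative SBRT followed by surgical resection at URMC". Feasibility is also primary objective 2.2(a).

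On numbers, Section 9 says "we plan to enroll 18 patients over 1-2 years with a goal of 12 evaluable cases". Section 3.1 repeats the target, and neither section defines evaluable. The Schema reads "Phase I: 12 patients who undergo SBRT and surgical resection". Section 9 times the acute toxicity evaluation by 12 patients who have had SBRT and resection, and adds "Long term safety and efficacy will be evaluated after all 12 patients have undergone surgical resection", with at least 6 months of follow-up or death.

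On patients who are not resected, Section 4.3.3 says "If surgical resection cannot be completed due to the presence of advanced disease, the patient will be withdrawn from the protocol at that time", with standard treatment and follow-up thereafter. The same section says "However if re-staging scans are obtained and demonstrate metastatic disease, surgery will not be performed", without giving the study status of those patients.

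On follow-up, Section 4.2(d) says "Patients will be followed at least every 6 months for a minimum of 5 years by a physician", and Section 6.2 places adverse event assessment "at the pre-operative evaluation visit and at follow up visits for at least 5 years". Neither makes an exception for withdrawn patients. The secondary objectives in Section 2.3 (local control and recurrence, PFS, OS) concern treated patients.

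The publication paragraph of Section 9 lists acute and late toxicity, surgical morbidity, and Kaplan-Meier survival outcomes. It lists no resection rate and names no analysis population.

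**The concern.** The patients whom Section 4.3.3 withdraws are not a random subset: they are those found to have advanced disease. If study data collection stops at withdrawal, their later deaths and late toxicities are unrecorded, and what remains describes a better-prognosis group than the treated patients of Section 2.3. Objective 2.3(a) also compares local control and recurrence with historical controls. The proton study described in Section 1 gives one-year survival and local progression for all 15 treated patients, including the 4 not resected, so a resected-only estimate from this trial would not be like for like.

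The feasibility question is separate. A trial that asks whether patients can have SBRT and then resection needs a denominator that includes those who do not reach resection. The plan describes only the 12 who do, and does not commit to reporting how many patients it took to get them.

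**Working it through.** **1. The plan's own figure.** 18 enrolled for 12 evaluable implies attrition of 1 − 12/18 = 33.3%. No rate or formula is given, so 18 cannot be derived, only checked for plausibility. The only resection rate in the documents is 11/15 = 73.3% (exact 95% CI 44.9 to 92.2), from the cited proton study with capecitabine; applying it here is an assumption. Then 12/(11/15) = 16.4, rounded up to 17, close to 18. The binomial chance of at least 12 resections among 18 patients is 0.82 at that rate. The 18-for-12 target is reasonable.

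**2. The resection rate by denominator** (Clopper-Pearson 95% intervals):

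| Denominator | Resected | Rate | 95% CI |
|---|---|---|---|
| The 12 target cases | 12/12 | 100%, by construction | not informative |
| 13 irradiated | 12/13 | 92.3% | 64.0 to 99.8 |
| 14 irradiated | 12/14 | 85.7% | 57.2 to 98.2 |
| 16 irradiated (16.4 from step 1, rounded) | 12/16 | 75.0% | 47.6 to 92.7 |
| All 18 enrolled | 12/18 | 66.7% | 41.0 to 86.7 |

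**3. How likely the case is to arise.** With independent patients and a constant resection probability p, the chance that at least one irradiated patient goes unresected before the 12th resection is 1 − p^12:

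- p = 11/15: 1 − 0.024 = 97.6%
- p = 0.90 (assumed): 1 − 0.282 = 71.8%
- p = 0.95 (assumed): 1 − 0.540 = 46.0%
- p = 1: 0

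Section 6.3 expects every patient to be resected and Section 7.2 expects nearly all, so the higher values of p are closer to the sponsor's stated view. These figures show how often the question comes up; they do not measure bias.

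**4. Follow-up provisions side by side.** Sections 4.2(d) and 6.2 are general and run at least 5 years. Section 4.3.3 takes one group out of the protocol. Appendix B lists follow-up visits with CA 19-9 and imaging, without limiting them to resected patients and without mentioning withdrawn ones. No section says whether withdrawal ends treatment under the protocol or data collection as well.

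**5. What each outcome needs.**

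- OS and late toxicity need observation after withdrawal. If that stops, they are incomplete in this group.
- PFS differs. When metastatic disease is the reason, the failure and its date are known at withdrawal. PFS is biased only if the patient is also left out of the analysis.
- The resection rate needs only counts. Enrolment and withdrawals with reasons go into the progress reports (Section 9, Appendix C), so it could be derived. What is missing is the commitment to report it.

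**The case against.** The strongest reply is that the documents already point to the right population. Objective 2.2(b) ties acute toxicity to SBRT, and Section 2.3 speaks of treated patients. The Section 9 sentences about the 12 say when to evaluate, not whom to include, and Appendix A, an acute toxicity form completed after resection, explains the wait. The list of outputs opens with a non-exclusive word, and the stated purpose makes it likely that a resection count would be given. All of that stands. A reader might infer that a resected-only analysis is planned; the documents do not say so. The lack of a definition of evaluable would, alone, be missing detail.

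A reader might also infer that withdrawn patients' data are discarded, or that Sections 4.2(d) and 6.2 promise 5 years of follow-up to every patient in flat contradiction of Section 4.3.3. Neither is supported. Section 4.3.3 says nothing about discarding data, care continues under standard follow-up, and 4.2(d) comes directly after an item on the post-resection visit, so it can be read as the course for those who complete the sequence. Nor does Section 5.1 show that unresected patients go without surveillance: its statement that no routine oncologic evaluation follows SBRT most naturally covers the short interval before surgery.

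What the reply does not remove is that nothing carries the treated population into Section 9, nothing says that data collection continues after withdrawal, and nothing commits to a resection rate.

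**Conclusion.** The concern holds as two limited gaps that should be fixed before the data are analysed.

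First, the withdrawal rule and the follow-up provisions are not reconciled. If withdrawn patients leave study follow-up, later OS and late toxicity are lost selectively in poor-prognosis patients. Bias in PFS requires the further step of excluding them from the analysis. The status of patients not operated on after restaging is unstated.

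Second, the stated purpose has no committed output. Within the 12 target cases the resection rate is 100% by construction; it is 75.0% with 16 irradiated and 66.7% with 18 enrolled. Those two figures rest, respectively, on the cited proton study's resection rate and on full enrolment with exactly 12 resections. Intervals are wide and the analysis is descriptive.

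The effect is zero if every irradiated patient is resected. A reader might take the gap between 18 and 12 as a sample size error, which it is not. Acute safety monitoring and the rule closing accrual are not in question.

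**What to change.** In Section 9:

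- Define evaluable, and keep 12 resected cases as the accrual target only.
- Add to the planned outputs the number resected within the protocol's own window, over all enrolled and over all who start SBRT, each with an exact 95% CI.
- State that SBRT toxicity, recurrence, PFS and OS are analysed in all patients who start SBRT, consistent with Sections 2.2(b) and 2.3, and surgical morbidity in those operated on.

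Reconcile Section 4.3.3 with Sections 4.2(d) and 6.2 and Appendix B, so that unresected patients, including those not operated on after restaging, stay in data collection for toxicity, progression and survival although off protocol treatment. Their standard follow-up can supply the data; clinical management and surveillance schedules need not change.

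The cost is a little more data collection on a few patients, and feasibility and survival figures that may look less favourable.

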## **6.        ADVERSE EVENTS**

### **6.1      Definition of Adverse Event**

An adverse event is any symptom, sign, illness, or experience which develops or worsens during the course of the study, whether or not the event is considered related to the study intervention.

The investigator will be responsible for assessing the etiology of any adverse events and determining if these can be considered a treatment related adverse event (TRAE) which arose directly or indirectly as a result of SBRT. Adverse events will be graded according to the NCI CTCAE Version 4.0. TRAE will be considered “acute” if they occur within 1-4 weeks post SBRT and prior to surgical resection and “late” if they occur after this time period.

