#### DATA SUMMARY:

1. ENROLLMENT			
Since last Report:	_____	Total to Date:	_____
Comments:			

2. ADVERSE EVENTS			
	Serious / Related / Unexpected  :	Other Serious  :	Non-Serious:
Since Last Report:			
Total:			
Comments:			

Serious, possibly/probably/definitely related events that are considered unexpected require prompt reporting to RSRB and DSMC.

Serious events which are unrelated and/or expected require reporting to the RSRB at least annually and to the DSMC per DSMC reporting requirements.

3. SUBJECT WITHDRAWALS				
	Investigator- initiated:	Reason(s):	Subject- initiated:	Reason(s):
Since last report:				
Total:				

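### Section 9 sets no automatic accrual hold for a death within 30 days after resection unless it appears directly due to SBRT, and states no committee review before the quarterly one if the death is judged unrelated or expected

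*Combined protocol and SAP*

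**What the plan says.** **Accrual hold (Section 9).** Recruitment stops and safety data are analyzed in two cases. One is "if there appears to be any grade 3 or greater toxicity on any subject that can be directly attributed to SBRT". The other is a patient losing eligibility for resection purely through SBRT toxicity. Two follow-on rules come next. The study closes to accrual if a patient becomes ineligible in that way. The investigators decide whether to continue after "grade 3 or greater toxicity directly attributable to SBRT that is reversible and ultimately able to undergo resection".

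**Attribution (Section 6.1).** A treatment-related adverse event is one "which arose directly or indirectly as a result of SBRT". "The investigator will be responsible for assessing the etiology of any adverse events" and for deciding whether they are treatment related.

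**Committee review (Section 9 and Appendix C).** Serious events that are related and unexpected are reported within 10 calendar days. "The DSMC Chair will determine whether further action is required, and when patient safety is of concern, an interim meeting may be called". Footnote 1 to the Appendix C data summary says that serious, "possibly/probably/definitely related events that are considered unexpected require prompt reporting to RSRB and DSMC". For two other combinations the rule is: "Serious adverse events that are related AND expected or unrelated AND unexpected will be reported to the Committee for review at the quarterly meeting". The quarterly progress report covers "serious adverse events both expected and unexpected". Footnote 2 in Appendix C sends unrelated and/or expected serious events to the DSMC under the DSMC's own reporting requirements, which are not reproduced.

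**Other safeguards.** Section 6.4 requires notice of every serious adverse event to the primary investigator within 24 hours, and IRB reporting under local policy. Section 9 has the investigators review data and safety continuously.

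**The concern.** Intraoperative and postoperative surgical morbidity is primary objective (c) in Section 2.2, and Section 4.3.3 places surgery within 3 weeks of the end of SBRT. In a single patient, radiation and surgical causes of a postoperative death may be hard to separate, and a death after a Whipple can reasonably be put down to the operation. The hold nevertheless depends on an attribution to SBRT, and a direct one, which is narrower than the protocol's own definition of a treatment-related event.

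The Background shows why the surgical period deserves its own trigger. The photon predecessor was ended early because of fibrosis found at operation and longer operating times. The proton predecessor's safety is summarized as no deaths or leaks within 30 days of surgery. Section 1 reports no known prospective experience of SBRT alone before resection, and Section 7 says the technique is new to the center.

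At stake is whether new patients keep starting SBRT while a postoperative death waits for a committee to see it beside the other surgical results.

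**Working it through.** There is no stated stopping boundary, error rate or power to reproduce. The check has two parts: reading the rules against a death after resection, and sizing the consequence.

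**1. Which rule catches a death within 30 days after resection?**

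| Investigator's judgement | Automatic hold? | Committee route in the protocol text |
|---|---|---|
| Directly due to SBRT | Yes | 10-day report and Chair decision if unexpected; quarterly if expected |
| Related only indirectly, unexpected | No | 10-day report and Chair decision |
| Related only indirectly, expected | No | Quarterly |
| Unrelated, unexpected | No | Quarterly |
| Unrelated, expected | No | Not listed separately; quarterly report, and DSMC requirements outside the documents |

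The ineligibility trigger cannot apply to a patient already resected. Neither follow-on rule fits: one concerns ineligibility, the other a reversible toxicity. So even a death that does stop recruitment has no stated path to a decision.

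**2. How often could this arise?**

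Inputs: 12 evaluable resected patients (Section 9) and 30-day mortality p. The documents give no planning value for p; their only figure is no deaths among the 11 resected in the proton series (Section 1). I assume p from 1% to 10% and independent patients.

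P(at least one death in 12) = 1 - (1 - p)^12

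| Assumed p | Calculation | Result |
|---|---|---|
| 1% | 1 - 0.99^12 | 11.4% |
| 2% | 1 - 0.98^12 | 21.5% |
| 3% | 1 - 0.97^12 | 30.6% |
| 5% | 1 - 0.95^12 | 46.0% |
| 10% | 1 - 0.90^12 | 71.8% |

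These count every 30-day death, including those that would already stop recruitment or reach the Chair through the 10-day report. At a given p they are therefore an upper bound on how often the gap matters. The documents give no attribution shares with which to narrow it.

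**3. How many patients enrol before a quarterly review?**

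Inputs: 18 enrolled over 1-2 years (Section 9), assumed even.

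- Per quarter: 18/4 = 4.5 (1 year) or 18/8 = 2.25 (2 years). This is the maximum.
- If the death falls at a random time between reviews, the average is half: 2.25 or 1.125.

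This treats each enrolment as an SBRT start.

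**4. What can a hold not reach?**

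On the planned schedule, SBRT start to a day-30 death takes at most 7 + 21 + 30 = 58 days (Sections 4.3.1a and 4.3.3). In that time 18 × 58/365 = 2.9 or 18 × 58/730 = 1.4 further patients enrol. A hold protects only those who have not yet started SBRT.

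**The case against.** The strongest reply is that the gap is narrower than the hold rule alone suggests. The primary investigator hears of any death within 24 hours and decides how to respond. The investigators review safety continuously, and serious events go to the IRB. The trigger needs only the appearance of a direct link to SBRT, so a suspicious death would already stop recruitment. Attribution-based triggers with quarterly oversight are a coherent choice for 12 evaluable patients, and the plan contradicts none of its own rules.

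Most of this stands and limits the point. It does not remove it: none of these provisions sets a hold, or a timed committee review, for a death judged unrelated or expected.

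Two stronger readings are tempting, and the documents do not support them.

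- A reader might infer that nobody outside the study team has to look at such a death for up to a quarter. Footnote 2 in Appendix C and Section 6.4 defer to DSMC and IRB rules that are not in the documents and may be stricter. What can be said is that the protocol text states no earlier committee review.
- A reader might take 11-72% as the frequency of unreviewed deaths. It is not: it includes deaths already covered, and its spread reflects the assumed mortality. Nothing in the documents supports 10% in particular.

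**Conclusion.** The concern holds in a limited form. Section 9 gives no automatic hold for a 30-day postoperative death unless it appears directly due to SBRT. For one judged unrelated or expected, the protocol text states no committee review before the quarterly one. The investigator's judgement of cause decides whether there is a hold, and helps decide which review route applies.

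The size rests on assumed mortality, even accrual and 12 resections: at most 11-72% of trials across 1-10% mortality, and at most 2.25-4.5 enrolments (1.1-2.3 on average) before the next quarterly review.

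One death would not show that SBRT is harmful, and the proposed hold is a trigger for review, not a stopping rule. It does not address excess non-fatal morbidity. This is a cheap improvement in patient safety that is worth making, not an error in any figure the plan states.

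**What to change.** Add to Section 9:

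*Any death within 30 days after resection, whatever its attribution or expectedness, is reported to the DSMC Chair within 10 calendar days of the study team learning of it. From the day the team learns of it, no new patient starts SBRT until the Chair has reviewed the death together with the Appendix A results available to date (out of resections done) and decided whether accrual resumes. The Chair decides within 10 calendar days of the report. A patient who has started SBRT has the individual discussion already described in this section. A patient who has finished SBRT proceeds to surgery unless the Chair or the surgeon advises otherwise.*

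**Cost.** The change is protocol wording and uses the existing Chair and form. The hold lasts at most about 10 + 10 = 20 days, which delays 18 × 20/730 = 0.5 to 18 × 20/365 = 1.0 enrolments. At least one hold would occur in 11-72% of trials across the assumed mortality range, sometimes when SBRT adds no harm. A new patient who cannot wait can have upfront surgery, which Section 1 describes as the usual choice. The Appendix A fields completed at the postoperative visit may still be blank for recent patients, so the Chair reviews what is available and does not wait for the rest.
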